It is well known that sleep is essential for brain development and maturation. Studies have shown that sleep-deprived young animals have smaller brains with loss of brain plasticity, which leads to diminished learning and adverse long-term behavioural effects. It is also established that infant massage improves sleep hygiene and is linked to the theory of environmental enrichment, which promotes brain development. Brain development during the first years of life depends on the quality of stimulation in the infant's environment. Early child development is a life-long determinant of health and well-being. There are significant societal and economic benefits from optimal infant cognitive development (2).

Protocol/Sponsor Number: GB02/17UCC Principal Investigator: [name]

5 Trial Objectives and Purpose

Primary objective

To assess the effect of a structured sensory enrichment programme on Infant sleep using qualitative and quantitate measures.

Secondary objective

To assess the effect of a structured sensory enrichment programme on neuro-development as assessed by a standardised neurodevelopmental assessment at approx. 4 months and approx. 18 months of age.

6 Description of protocol methodology

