6.2 Subjects

A total of 200 full term healthy infants will be studied. Recruitment will take place at CUMH and UCL-ICH London.

Inclusion criteria for participant selection are:

- Infants born > 37 weeks gestation
- Single births
- Not requiring admission to the Neonatal Unit
- Healthy infants without suspected congenital or metabolic anomalies

Exclusion criteria for participant selection are:

[figure not shown]
- Infants born < 37 weeks gestation
- Multiple births

Page 6

• Severe metabolic or genetic anomaly that would require ongoing specialist care in the infancy period.

Admission to the Neonatal Unit.6.2.1 Figure 1 Flow chart design of study

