7.3 Sensory enrichment programme including infant massage

A total of 200 full term healthy infants will be recruited. Recruitment will take place at CUMH and UCL-ICH London. Parents will be invited to provide proxy consent for their infant to participate and also for their own participation in the BabySMART study.

Once Day 2 screening assessment is complete, parents will be informed that the next appointment will be in approximately 2 - 3 weeks and that a member of the BabySMART team will contact them to schedule this appointment. Randomisation will occur at this visit. Participants will be randomised to either a structured sensory enrichment programme including infant massage (intervention arm) or to the control arm.

The massage will be applied according to IAIM (International Association of Infant Massage). Created in 1976 by Vimala McClure, it is the first global organisation with a professional programme which is run in several countries around the world, due to its proven benefits. The purpose of IAIM is to create a nurturing touch and communication through training, education and research so that parents, caregivers and children are loved, valued and respected throughout the world community.

At the 2 week visit parents will be provided with training in infant massage by an instructor who has completed a Baby Massage Ireland trainer course. The massage should be carried out daily until the 4 month visit. Massage training will be completed on-site in the INFANT Research Centre in the new Paediatric unit in the CUH and the JOHNSON'S® HEAD-TO-TOE® extra moisturizing baby cream will be supplied at these appointments

Mothers will be informed about the enrichment programme which will include the benefits of baby massage, infant cues, duration of application, points of care for application and application technique at this stage. The technique of massage application will be shown to the mother by the researcher using a model baby (doll).

Mothers will be asked to apply the massage on their own baby as instructed and they will be observed to determine whether they applied the massage correctly or not. Training will be reinforced both at the training session and by the provision of a training DVD which will be provided to parents.

Baby massage education will also be given at drop in classes where a review of the strokes will be undertaken. Each parent's application of baby massage will be observed and evaluated for correct

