7.5 MiChild Mobile Application

MiChild is a mobile application which is to be used by registered users only for the capture, storage and analysis of sleep and feeding. The aim of this app is to provide researchers working on the BabySMART study with a view of key infant data from birth to 4 months. The application is not mandatory and the parents can choose to record the information in a paper format in the diary that has been designed for the study. MiChild will provide a data capture tool where parents can capture in real time details on infant sleep, adherence and acceptance of the sensory enrichment programme and limited feeding data. The data inputted by parents will be available to them in an aggregated view allowing them to review weekly sleep and feeding.

This secure, multi-platform (Android & iOS) mobile solution will provide parents/guardians with the ability to capture an accurate and real-time view of their infant's sleep and feeding from birth. As well as the above, the application will also allow communication between parents and BabySMART research staff via a messaging option.

This application will be available through the apple app store and google play store. The application will only be accessible to parents who have a registered account created by research staff working on the BabySMART Study.

Registered users of the app will be created by research staff with the necessary privileges through an administrative application. These registered users will be provided with a random password by the BabySMART research staff at time of registration. This password will be stored in the database encrypted using industry standard Advanced Encryption Standard – Cipher Block Chaining (AES-CBC) which will have a 256-bit key for encryption. The registered user of the app will have to enter a "MiChild" user ID which is unique to the app and is created by the BabySMART research staff. This ID combined with their password allows a user's access to the application. At any stage throughout the use of the application, clinical staff can deactivate an account and therefore render the app un-usable by the users.

All data will be stored in University College Cork, on University College Cork servers. These servers will have restricted access to INFANT IT personnel only. All data on these servers will have restricted access insofar as it will be restricted to BabySMART research staff only so as to protect patient confidentiality.

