Is your baby fed on a regular schedule eg. every 4 hours?
Yes, always
Yes, try to

No, fed on demand	
If giving solid foods, how old was he/sh	he when they first had solids?
Age (weeks)	
Have you given your baby any vitaming	s or supplements since your last visit?
Yes	
No	
If yes, please provide details	
Does your baby use a soother/dummy	?
Yes, regularly	
Yes, occasionally	
No	
Sleeping	
Sleeping Arrangements	
Infant cot in separate room	
Infant cot in parent's room	
In parent's bed	
Infant cot in room with sibling	
Other, please specify	
Sleeping Position	
On his / her belly	
On his / her side	
On his / her back	
Sleeping time during the day (between	າ 7am and 7pm)

Protocol/Sponsor Number: GB02/17UCC Principal Investigator: [name]

Hours

Sleeping time during the night (between 7pm and 7am) Hours
How long does it take to put your baby to sleep in the evening? Hours Minutes
Wakefulness time between 10pm and 6am Hours
How does your baby fall asleep?
While feeding
Being rocked
Being held
In bed alone
In bed near parent
When does your baby usually fall asleep at night (24 hour format)? Time
Do you consider your baby's sleep a problem?
A very serious problem
A small problem
Not a problem
Is it always the same person that puts the baby to bed?
Yes
No

If yes, who is it?	
Mother	
Father	
Other person	
Does the baby move in his/her sleep? Yes No	
The things that disturb my baby's sleep are: (tick a	ill that apply)
Any sound, even very soft sounds	
Radio or TV	
People talking	
Phone ringing	
Other	
Nothing disturbs my baby's sleep	
When my baby wakes up he/she is usually:	
Fussy	
Crying	
Hungry	
Alert but quiet	
Alert and active smiling when I app	proach
Other	
My baby can help calm him/herself to sleep by:	
Sucking on thumb or fingers	

	Holding a favourite blanket or soft	toy		
	Sucking on a soother/dummy			
	Other			
When my baby	needs help at night to calm down Pick him/her up	l:		
	Try talking and gently rubbing his/	her back		
	Play music for him/her			
	Let him/her cry before I go in			
	Give him/her a soother/dummy or	a bottle		
	Other			
I feel the best way to help my baby sleep through the night is to:				
	Stick to the same bedtime routine			
	Feed my baby shortly before putti	ng him/her	to bed	
	Let my baby cry him / herself to slo	еер		
	Comforting my baby whenever it's	needed		
	Nothing I do seems to help			
	Other			
Do you know w	hat sleep training is?			
	Yes			
Have you tried	sleep training?			
	Yes, The Cry it Out approach			

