How often do you bath you	r baby?
Once a week	
2-3 times a week	
3-5 times a week	
Daily	
Other, please specify	
What do you use in the bath Please specify product name	
How often do you moisturis	e your baby's skin?

Never
Once a week
2-3 times a week
Daily
Several times a day
Occasionally
What do you use to moisturise your baby's skin? Please specify product name and brand
Feeding
Does your child still take a bottle?
Yes
No
If Yes, how many bottles a day do they take of the following
Infant formula
Growing up milk
Cow's milk
• Other
If other please specify
Does your baby use a soother/dummy?
Yes, regularly
Yes, occasionally
No L
Sleeping
Sleeping Arrangements
Infant cot in separate room

Infant cot in parent's room
In parent's bed
Infant cot in room with sibling
Other, please specify
Sleeping Position
On his / her belly
On his / her side
On his / her back
Sleeping time during the day (between 7am and 7pm) Hours
Sleeping time during the night (between 7pm and 7am) Hours
How long does it take to put your baby to sleep in the evening? Hours Minutes
Wakefulness time between 10pm and 6am Hours
How does your baby fall asleep?
While feeding
Being rocked
Being held
In bed alone
In bed near parent
When does your baby usually fall asleep at night (24 hour format)?
Time

Do you consider your baby's sleep a problem?					
A very serious problem					
A small problem	A small problem				
Not a problem					
Is it always the	same person that puts the baby to bed?				
	Yes				
	No				
If yes, who is it?	Mother				
	Father				
	Other person				
Does the baby r	move in his/her sleep?				
	Yes No				
The things that	disturb my baby's sleep are: (tick all that	apply)			
	Any sound, even very soft sounds				
	Radio or TV				
	People talking				
	Phone ringing				
	Other				
	Nothing disturbs my baby's sleep				
When my baby	wakes up he/she is usually:				
	Fussy				

	Crying	
	Hungry	
	Alert but quiet	
	Alert and active smiling when I approach	
	Other	
My baby can he	elp calm him/herself to sleep by:	
	Sucking on thumb or fingers	
	Holding a favourite blanket or soft toy	
	Sucking on a soother/dummy	
	Other	
When my baby needs help at night to calm down I:		
	Pick him/her up	
	Try talking and gently rubbing his/her back	
	Play music for him/her	
	Let him/her cry before I go in	
	Give him/her a soother/dummy or a bottle	
	Other	
I feel the best way to help my baby sleep through the night is to:		
	Stick to the same bedtime routine	

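### Night wakefulness, day sleep and night sleep are asked in hours only while settling time has hours and minutes; adding a minutes field is a nearly free gain in precision, mainly at 18 months

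*Combined protocol and SAP*

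**What the plan says.** The Sleeping section of the 4-month questionnaire (protocol Appendix) has four duration items, and the 18-month questionnaire repeats them.

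- Day sleep: "Sleeping time during the day (between 7am and 7pm) Hours" (intact on the 18-month form; on the 4-month form a page break separates the label from its unit).
- Night sleep: "Sleeping time during the night (between 7pm and 7am) Hours".
- Settling time: "How long does it take to put your baby to sleep in the evening? Hours Minutes".
- Night waking: "Wakefulness time between 10pm and 6am Hours".

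Only settling time has a minutes field. Neither form states a precision or a rounding rule.

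The primary objective (section 5) is "To assess the effect of a structured sensory enrichment programme on Infant sleep using qualitative and quantitate measures". It names no variable, and nothing designates these items as an endpoint. Section 7.2 adds a sleep EEG at about 4 months, timed around the longest daytime nap. Section 7.5 adds parent entry by app or paper diary from birth to 4 months: "MiChild will provide a data capture tool where parents can capture in real time details on infant sleep". At 18 months the protocol describes no sleep measure other than the questionnaire.

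**The concern.** The form asks for minutes on one short duration and omits them on another directly beside it. Because the same layout appears on both forms, a fault in reading the PDF is an unlikely explanation. A parent whose baby is awake for 20 or 40 minutes a night can write 0, 1 or a decimal, and different parents will choose differently. That is avoidable measurement error, and it is largest relative to the signal when the quantity itself is short. Minutes that were never recorded cannot be recovered at analysis.

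**Working it through.** **Inputs.** Section 6.2: "A total of 200 full term healthy infants will be studied". Section 7.3 gives two arms: "Participants will be randomised to either a structured sensory enrichment programme including infant massage (intervention arm) or to the control arm". The allocation ratio is not stated, so 1:1 (100 per arm) is assumed. Two-sided alpha of 0.05, no dropout, and every mean, SD and effect below are also assumptions. The protocol has no sample-size calculation to reproduce.

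**Step 1: variance added by rounding.** Rounding to a width of w hours adds about w²/12. For w = 1 that is 1/12 = 0.083 h², an SD of 0.289 h or 17 minutes per infant. The inflation factor is 1 + 1/(12·SD²).

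**Step 2: power, normal approximation.** Choose the effect that gives 80% power with unrounded data, which is 0.396 SD at 100 per arm. Power after rounding is Φ(2.802/√inflation − 1.960). At SD 0.5 h, for example, inflation is 1.333 and power is Φ(2.802/1.155 − 1.960) = Φ(0.467) = 68%.

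| Assumed SD (h) | Inflation, whole hours | Power, whole hours | Power, half hours |
|---|---|---|---|
| 0.5 | 1.333 | 68% | 77% |
| 0.75 | 1.148 | 74% | 79% |
| 1.0 | 1.083 | 77% | 79% |
| 1.5 | 1.037 | 79% | 80% |
| 2.0 | 1.021 | 79% | 80% |

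If day and night sleep have an SD of 1 h or more, whole-hour entry therefore costs about 1 to 3 points.

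**Step 3: simulation for night waking.** Short waking times are skewed and bounded at zero, so Step 2 is only a guide. I simulated 20,000 trials with 100 per arm, gamma-distributed wakefulness, a true 25% reduction and a two-sample t-test. Results vary by up to about a point between runs.

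| Assumed control mean, SD (h) | Exact | Half hour | Nearest hour | Rounded down |
|---|---|---|---|---|
| 0.75, 0.6 | 71% | 68% | 62% | 58% |
| 0.5, 0.5 | 52% | 48% | 43% | 36% |
| 1.5, 1.0 | 86% | 85% | 82% | 82% |

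In the first two rows whole-hour entry loses 9 points (71 − 62; 52 − 43) if rounded to the nearest hour, and 13 to 16 points (71 − 58; 52 − 36) if rounded down. Half-hour entry loses 3 to 4. In the third row the losses are 1 to 4 points.

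The share of control infants recorded as zero is 42% (nearest hour) or 74% (rounded down) in the first row, and 63% or 87% in the second.

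**The case against.** The strongest reply is that an hours label is a unit, not a rounding instruction. Nothing on either form forbids 0.5 or 1.25. A reader might infer from the layout that whole-hour rounding is built in and that power is therefore lost; the documents do not support that. Whole-hour entry is a risk, and if parents write half hours the loss is 1 to 4 points in every scenario above. This part of the objection stands.

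Three further points also stand.

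- The exact-minutes comparator is idealised. Parents recalling a night will probably still cluster at quarter or half hours, so the real gain from a minutes field is smaller than the tables show.
- A reader might set the 17-minute rounding SD beside a plausible treatment effect and call them similar. That compares one infant's error with a difference in means. At 100 per arm, nearest-hour rounding adds a standard-error component of √(2/(12·100)) = 0.041 h, about 2.4 minutes.
- A reader might infer that the primary endpoint is compromised. No endpoint variable is named, the app or diary also captures sleep up to 4 months, and section 5 ties the 18-month visit explicitly only to neurodevelopment, the secondary objective.

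The objection does not remove the inconsistency between adjacent items or the lack of a stated precision. Nor does the parallel-source argument cover every case: the EEG follows a daytime nap and cannot measure night waking, and the app and diary stop at 4 months.

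**Conclusion.** The point holds as a minor data-capture improvement. The layout is certain; its consequence is conditional. If night waking is short (assumed mean 0.5 to 0.75 h, SD 0.5 to 0.6 h) and parents enter whole hours, the loss is about 9 to 16 power points at 100 per arm; with half-hour entry it is about 3 to 4. At mean 1.5 h and SD 1.0 h it is about 4 points or less. For day and night sleep the loss is small, so minutes there are a matter of consistency more than power.

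All of this rests on assumed distributions, a 25% reduction, 1:1 allocation, two-sided 0.05 and no dropout; the protocol supplies only the total of 200. The practical weight falls on 18 months, where no finer source of sleep data is described.

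**What to change.** On the 4-month and 18-month questionnaires, add a minutes field to the 10pm to 6am wakefulness item and, for consistency, to day sleep and night sleep, in the format settling time already uses. Make the same change wherever these answers are entered, and analyse all of them in minutes.

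The cost is three extra fields on each of two forms, the matching entry fields, and an amendment recorded under section 12. No visit or procedure changes. The benefit reaches only forms completed after the change, so answers given on the old layout should be kept as written and identified by form version.
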